Dietary modification represents an intriguing potential MS intervention. **One aspect of diet that shows promise involves calorie intake.** Calorie restriction or fasting prior to the induction of experimental autoimmune encephalomyelitis (EAE), a mouse model of MS, is associated with a less aggressive course.^{11,12} There may be several mechanisms by which this occurs. **Calorie restriction and fasting are associated with reductions in pro-inflammatory cytokines** and other inflammatory markers in EAE mice^{11,12} and in humans who are healthy, obese, or have asthma, similar reductions have been observed.¹³⁻¹⁶ Ceramides are elevated in MS patients and pathogenic in vitro;¹⁷ calorie restriction reduces their levels in humans without MS.¹⁵ Calorie restriction also reduces markers of oxidative stress,¹⁵ and thus may reduce mitochondrial dysfunction. Beyond its direct biological effects, optimization of weight may lead to improvements in MS-related symptoms such as fatigue as well as in health-related quality of life, as overweight MS patients have been shown to have lower self-rated measures of well-being than controls.^{18,19} As such, **there is a strong rationale for evaluating the benefits of calorie restriction in MS.** The timing of calorie intake may also be critical, suggesting a possible rationale for consolidating the time period in which typical calories are consumed.

2. Study Procedures

a. Study design, including the sequence and timing of study procedures

Calorie restriction study:

Overview: We will conduct a pragmatic pilot study in which 80 patients with MS who are undergoing monthly infusions with natalizumab and who are overweight or obese are offered enrollment in this trial. Participants who consent will undergo a basic evaluation of total energy expenditure. At baseline, participants will participate in a short training about intermittent versus continuous calorie restriction and will choose the dietary intervention they'd prefer to use. The LoseIt! Application will be installed on the participants' smartphones, and they will receive training in utilizing the application. Baseline assessments of health-related quality of life (HRQoL), fatigue, self-esteem and physical activity will be conducted. Serum and plasma will be collected for future studies.

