Participants will then be randomized to one of two groups: 1) to receiving weekly educational text or email messages about the positive health effects of maintaining a normal body mass index, particularly as it relates to MS, or 2) standard of care (no additional contact). At the routinely-scheduled infusions at months 3 and 6, body mass index, waist circumference, and fatigue/HRQoL/self-esteem will be evaluated. Serum and plasma will be collected for future studies.

Enrollment and Randomization: In order to maximize enrollment within the period of support, people with MS who receive monthly natalizumab infusions and meet other criteria (see #3 inclusion/exclusion criteria) will be offered participation in the study. Potential participants may be notified when receiving their regularly scheduled appointment reminder phone call that a study team member may approach them during their upcoming infusion visit about enrollment in the study. The Johns Hopkins MS Center infusion center currently provides natalizumab infusions for

Date: 7/20/16

Principal Investigator: [name], MCR

Application Number: IRB00095554

140 MS patients per month; it is estimated that two-thirds have a body mass index ≥ 25 kg/m². Participants will be randomized by the study statistician 1:1 to the frequent patient activation arm or standard of care.

Study Procedures/Schedule of Events:

Patients will be consented one month prior to the baseline visit so they can be given adequate notice and can be given a stool sample collection kit to bring it at their next infusion. At the consent visit, baseline energy requirement will be determined (see below) and the patient's waist circumference will be measured. Waist circumference will be measured according to NIH protocol (patient standing with feet shoulder width apart, arms crossed over chest, and abdominal muscles relaxed, with measurement taken at the top of the iliac crest, at the end of normal expiration).

At the baseline visit, the following will be done:

- Vital signs and waist circumference
 - i. If waist circumference varies $\geq 10\%$ from the consent visit, baseline energy requirement will be re-calculated
- Patient-Determined Disease Steps

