- Health-related quality of life, (Functional Assessment in MS [FAMS]), fatigue (PROMIS fatigue), Pittsburgh Sleep Quality Index (PSQI), timing of sleep (Morningness-Eveningness Questionnaire [MEQ]), self-esteem (Rosenberg Self-Esteem Scale) and physical activity (International Physical Activity Questionnaire) assessments
- Blood for future research collected (30 ml)
- Coaching about the two diet options
- Installation of LoseIt! application on smartphone
- Determination of baseline energy requirement (*see below*)
- Randomization group assigned (participant blinded)
- Stool sample kit collection

At follow-up visits (months 3 and 6), the following will be done:

- Vital signs and waist circumference
- Patient-Determined Disease Steps (month 6 only)
- Health-related quality of life (Functional Assessment in MS [FAMS]), fatigue (PROMIS fatigue), Pittsburgh Sleep Quality Index (PSQI), timing of sleep (Morningness-Eveningness Questionnaire [MEQ]), self-esteem (Rosenberg Self-Esteem Scale) and physical activity (International Physical Activity Questionnaire) assessments
- Blood for future research (30 ml/visit)
- Stool sample kit distribution (at month 3) and collection (at month 6)
- Collection of LoseIt! application data (calorie counts) since prior visit

Determination of Baseline Energy Requirement and Diet Details: The baseline energy requirement (total energy expenditure) of each participant will be determined prior to randomization. This measurement is defined as the number of calories needed to maintain the current body weight. Total energy expenditure will be assessed using validated equations from University of Arizona Calorie Need Estimates, which include an individual's estimated resting

Date: 7/20/16

Principal Investigator: [name], MCR

Application Number: IRB00095554

energy expenditure (based on current weight, height and age) and physical activity (based on the International Physical Activity Questionnaire short form).

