Participants will receive education about two diet approaches: intermittent calorie restriction and continuous calorie restriction. For the intermittent calorie restriction group, a standardized percentage reduction to 25% of the baseline energy requirement will be used two days a week. For the continuous calorie restriction group, the same percentage calorie reduction will be provided, but the restriction will take place over an entire seven-day period (i.e. the group will be provided with food containing 78.6% of their baseline energy requirement (calories) each day. All participants will be encouraged to drink water liberally to stave off hunger. If a participant in one group is unable to follow their chosen diet, rather than losing the subject as a drop-out, the subject will switch to other dietary approach.

Adherence Intervention: All subjects will be asked to document adherence using the LoseIt! application, which tracks calorie intake based on food items and quantity consumed. The application will be installed on the subjects' smartphones at the baseline visit, and they will be instructed how to use it.

Subjects will be randomized 1:1, stratified by week of enrollment, to receive electronic adherence support or to the standard of care (no additional contact). The stratified randomization was chosen because participants often receive their infusions at the same time due to the 28-day dosing schedule, and thus may otherwise discuss their impressions of the study with other participants who happen to be infused at the same time. Those who are in the intervention arm will be sent a text message once a week providing encouraging information about the health benefits of weight loss and, where possible, specifically focusing on how it may benefit their MS. They will be asked to send the previous week's log of calories consumed to the research group (this information is readily available using the LoseIt! application).

Calorie Timing Study

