Age 18-75 years; meets 2010 criteria for MS	To ensure broadly generalizable to the MS patient population
Body mass index (BMI) < 25 kg/m ² , or if higher, participant was unwilling to enroll in calorie restriction study	Only want to enroll overweight or obese individuals if they are unwilling to restrict calories, as calorie timing study unlikely to lead to weight loss
No history of diabetes requiring medication	To avoid unpredictable hypoglycemia
Not pregnant, willing to avoid becoming pregnant during the study, and not breastfeeding	To avoid danger to fetus or threats to milk supply or health
No history of an eating disorder	To prevent relapse of eating disorder
No current use of warfarin	To avoid INR fluctuations
No history of major surgery within past 3 months	To prevent improper wound healing
Have a smart phone with the capability of taking and storing photographs	To provides study team with time stamps indicating timing of oral intake.

4. Drugs/ Substances/ Devices

- a. The rationale for choosing the drug and dose or for choosing the device to be used. N/A
- b. Justification and safety information if FDA approved drugs will be administered for non-FDA approved indications or if doses or routes of administration or participant populations are changed. N/A
- c. Justification and safety information if non-FDA approved drugs without an IND will be administered. N/A

5. Study Statistics

a. Primary outcome variable.

Calorie restriction study: Change in waist circumference

Calorie timing study: Change in metabolism biomarkers

b. Secondary outcome variables.

Calorie restriction study: Change in body mass index, number of pounds lost, percentage adherence to recommended calorie intake, changes in health-related quality of life, changes in fatigue and sleep

Calorie timing study: Adherence to photographing foods, changes in health-related quality of life, fatigue, and sleep

c. Statistical plan including sample size justification and interim data analysis.

Summary statistics (mean \pm standard deviation, median and interquartile range, or number and percentages) will be used to describe the outcomes.

Calorie Restriction:

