For the primary objective, the impact of increased patient engagement via the smartphone on weight loss (pounds lost, change in body mass index, and change in waist circumference) as well as on the percentage adherence to the recommended calorie intake (as assessed by LoseIt! logs) will be evaluated in t-tests. If there are baseline imbalances in potentially meaningful covariates despite randomization, multivariate approaches accounting for imbalanced covariates will be employed.

For the secondary objective, the primary analysis will evaluate the association of weight loss (change in body mass index as well as change in waist circumference) with changes in health-related quality of life, sleep and fatigue using multivariate linear regression adjusted for age, sex, race, change in physical activity and baseline disability. Whether group assignment (extra smartphone engagement or standard of care) influences this relationship will also be evaluated.

The rationale for measuring change in waist circumference as the primary outcome is that waist circumference, rather than body mass index, is considered a better measure of the risk of metabolic syndrome.²⁰ However, for comparability with previously-published studies and in order to further evaluate the relationship between waist circumference with body mass index, both measures will be obtained.

Calorie Timing:

Metabolomics will be conducted on samples from the participants to evaluate the impact of restricting the hours in which foods are consumed. Primary analyses will be intent-to treat; secondary analyses will investigate with the actual time of day metrics, as assessed by time stamps of smartphone photos, are predictive of changes in metabolism. Secondary outcomes will be assessed as above.

d. Early stopping rules.

Participants who become pregnant, experience weight loss with BMI < 20 kg/m², or who develop another issue that, in the estimation of the investigator, puts them at risk of ongoing participation, the participant will be asked to cease following the diet but will be followed to the completion of the study.

6. Risks

a. Medical risks, listing all procedures, their major and minor risks and expected frequency.

- Calorie-restriction diet
 - The risks associated with the diets are not known
 - Previous studies of similar diets in humans have not shown any serious risks.
 -

-
- Calorie timing diet
 - Participants may be hungrier in the time in which foods are not being consumed

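### The calorie restriction t-tests name no visit for change and no method for missing outcomes, so outcome-related dropout that differs between arms would bias the primary comparison.

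*Combined protocol and SAP*

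**What the plan says.** Section 5a gives the primary outcome as "Calorie restriction study: Change in waist circumference", without a time point. Section 5c (Calorie Restriction) states that the effect of messaging on pounds lost, BMI, waist and percentage adherence "will be evaluated in t-tests". The only extension is adjustment for covariates that turn out imbalanced at baseline.

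Two follow-up measurements exist. The overview in section 2a says "At the routinely-scheduled infusions at months 3 and 6, body mass index, waist circumference, and fatigue/HRQoL/self-esteem will be evaluated", and the schedule of events lists vital signs and waist at both visits.

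The randomised difference is one of contact. "Those who are in the intervention arm will be sent a text message once a week", and they are also asked to submit the past week's calorie log. The other arm is assigned "or to the standard of care (no additional contact").

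For this study the plan gives no analysis set, missing-data method, sensitivity analysis or expected dropout rate. Intent-to-treat is mentioned only under Calorie Timing.

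**The concern.** A t-test on change needs one change score per person. Someone without a value at the chosen visit has no score and leaves the test unless it is imputed, and no imputation is described. Covariate adjustment does not help, because it also needs an observed outcome. If the visit is month 6, a participant measured at month 3 and then lost contributes nothing.

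This matters for the comparison between arms because the intervention is itself contact with the study team, which may affect who stays. The plan also recognises that failing the diet can lead to dropout, since it offers a switch of diet to prevent this. If people doing poorly leave one arm more often than the other, those who remain are no longer comparable, and the primary comparison shifts by an amount that the t-test can neither show nor correct.

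**Working it through.** **Inputs from the documents.** The target is "80 patients with MS who are undergoing monthly infusions with natalizumab and who are overweight or obese", randomised 1:1, so 40 per arm if all 80 enrol. Waist is measured at months 3 and 6. No SD, effect size, alpha, power or dropout rate is given, so the plan has no figure to reproduce here.

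**Assumed inputs.** SD of change σ = 6 cm; correlation of month 3 with month 6 change ρ = 0.7; all dropout after month 3. A participant leaves when a latent score passes a cut-off c, set so that a fraction p leaves. The score has correlation k = 0.7 with a poor month 3 result. Change is follow-up minus baseline, so a positive bias in messaging minus control counts against messaging.

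**Step 1: bias of the month 6 t-test, dropout driven by month 3.** Those who stay look better by σ·ρ·k·λ(p), where λ(p) = φ(c)/(1 − p) and c = Φ⁻¹(1 − p).

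- λ(0.05) = 0.1031/0.95 = 0.109
- λ(0.10) = 0.1755/0.90 = 0.195
- λ(0.30) = 0.3477/0.70 = 0.497

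Bias = σ·ρ·k·[λ(control) − λ(messaging)].

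- Control 10%, messaging 5%: 6 × 0.49 × (0.195 − 0.109) = 0.25 cm, or about 0.3 cm. The t-test's nominal standard error is 6 × √(1/36 + 1/38) = 1.40 cm, so this is about 0.2 standard errors.
- Control 30%, messaging 10%: 6 × 0.49 × (0.497 − 0.195) = 0.89 cm, or about 0.9 cm. The standard error is 6 × √(1/28 + 1/36) = 1.51 cm, so this is about 0.6 standard errors.
- Arms exchanged: same size, opposite sign.
- Equal dropout in both arms, or k = 0: no bias.

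**Step 2: simulation (6,000 runs per scenario, two-sided 5% level, same ρ and k).** At 30% control versus 10% messaging with no true effect, the t-test is biased by 0.153 SD (0.153 × 6 = 0.92 cm) and rejects in about 10% of runs. A likelihood estimate using both visits is biased by 0.005 SD and rejects in about 5%. At a true benefit of 0.63 SD (3.8 cm), the t-test has 80% power with complete data and 51% here. With the two dropout rates exchanged, the t-test rejects in 89%, because the bias now exaggerates the benefit.

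**Step 3: dropout driven by the unseen month 6 value.** The t-test bias is 6 × 0.7 × 0.302 = 1.27 cm, or about 1.3 cm. The simulated likelihood bias is 0.12 × 6 = 0.7 cm. Rejection rates under no effect are about 14% and 8%. The model reduces the bias without removing it.

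**Step 4: precision when dropout is unrelated to outcome.** Both methods are unbiased. With n₁ and n₂ completers, the t-test variance is σ²(1/n₁ + 1/n₂). The likelihood variance is approximately σ²[(1 − ρ²)(1/n₁ + 1/n₂) + ρ²(1/40 + 1/40)].

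- 10% versus 20%: 1/36 + 1/32 = 0.0590, against 0.51 × 0.0590 + 0.49 × 0.05 = 0.0546, about 8% lower.
- 10% versus 30%: 1/36 + 1/28 = 0.0635, against 0.51 × 0.0635 + 0.0245 = 0.0569, about 10% lower.
- 5% versus 10%: 1/38 + 1/36 = 0.0541, against 0.51 × 0.0541 + 0.0245 = 0.0521, about 4% lower.

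When dropout follows the month 3 result, the two simulated SDs are about equal (0.243 SD each at 10% versus 30%). The gain there is in bias, not precision.

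**The case against.** Several stronger readings are tempting, and the documents do not support them.

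- A reader might infer that the plan prescribes a completer analysis. It does not; it is silent. Leaving out people without a value is what the named test does by default, and a t-test could be run on imputed data.
- A reader might infer that month 3 data are certainly wasted. No visit is named, so this holds only if change means month 6.
- A reader might infer that unequal dropout alone biases the result. It does not: at 10% versus 30% unrelated to outcome the simulated bias is about 0.
- A reader might infer that a real benefit of messaging would be hidden. The messaging arm has the extra task of sending weekly logs and could lose more people, which would reverse the bias.

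The plan also has real safeguards. Follow-up takes place at scheduled infusion appointments (section 2b). Both arms get visit reminders (section 2c), so the control arm is not wholly without contact. Participants who cannot follow one diet may switch to the other (section 2a). Those asked to stop the diet are followed to the end (section 5d). Stopping the diet therefore need not mean a missing waist. Section 2f, however, allows removal from the trial on overlapping grounds, and it must be reconciled with section 5d.

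These safeguards lower the risk. They do not say how the remaining missing values are analysed. The study is described as a pilot, which limits the stakes, but with 40 per arm there is little information to spare.

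**Conclusion.** The point holds in a limited form. The firm defects are an unnamed visit and no method for missing outcomes, under a test that drops anyone without a value. Bias requires dropout that is both unequal between arms and related to outcome. The difference in contact makes that plausible; nothing in the documents shows that it will happen or which way it would go.

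The figures of 0.3 to 0.9 cm rest entirely on the assumed SD, correlation, dropout rates and dropout mechanism. They illustrate the size and are not a forecast. Low or balanced dropout would make the bias negligible. The change is still worth making because the month 3 data are already being collected and the better analysis needs nothing new from participants.

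**What to change.** For waist, weight and BMI, replace the t-test in section 5c with a mixed model for repeated measures on all randomised participants, analysed as assigned. Months 3 and 6 are the outcomes; the terms are baseline value, arm, visit and arm-by-visit. State in section 5a that the month 6 arm contrast is the primary result. Say which baseline waist is used, since it is measured at both the consent and the baseline visit.

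Add one sensitivity analysis in which participants without a month 6 value are assumed to have returned to baseline.

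The cost is a paragraph of analysis text and a standard model, with no extra visits or data. The downside is reliance on missing at random. If dropout depends on unseen month 6 values, the model only reduces the bias (about 1.3 to 0.7 cm at 30% versus 10% in the illustration), which is why the sensitivity analysis is needed. Percentage adherence comes from self-entered app logs, so this model does not cover it and it needs its own rule for missing logs.

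### Calorie restriction study: the primary comparison is an unadjusted t-test on change in waist, with covariates added only after an undefined baseline imbalance; one prespecified model on baseline waist would be better at almost no cost

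*Combined protocol and SAP*

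**What the plan says.** Section 5a names the primary outcome: "Calorie restriction study: Change in waist circumference". Section 5c (Calorie Restriction) lists pounds lost, change in body mass index, change in waist circumference and percentage adherence as the measures to be compared between arms, and ends: "as assessed by LoseIt! logs) will be evaluated in t-tests". No covariate is named for that test. The next sentence is the conditional clause: "If there are baseline imbalances in potentially meaningful covariates despite randomization, multivariate approaches accounting for imbalanced covariates will be employed".

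No section defines imbalance, lists the potentially meaningful covariates, states the adjusted model, or says whether the unadjusted or the adjusted result is primary. The only fixed covariate list in 5c belongs to the secondary objective, the association of weight loss with quality of life, sleep and fatigue, which is "adjusted for age, sex, race, change in physical activity and baseline disability".

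Baseline waist is available. The baseline visit for this study in Study Procedures 2a includes "Vital signs and waist circumference", and waist is measured again later: "At the routinely-scheduled infusions at months 3 and 6, body mass index, waist circumference". Section 5 does not say which of the two follow-up visits defines the change.

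The overview in 2a gives the size and nature of the study: "We will conduct a pragmatic pilot study in which 80 patients with MS". No alpha, power, effect size, SD or correlation is stated.

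**The concern.** Two things are given up.

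- **Precision.** The change score subtracts baseline waist with a fixed coefficient of 1. A regression on baseline waist estimates that coefficient from the data and, in large samples, is never less precise. Under the plan, baseline waist can be a covariate only if it happens to be judged imbalanced.
- **A fixed analysis.** Two statisticians following 5c could report different primary results from the same data, because the threshold, the covariates and the ranking of the two results are all left open. How often the clause applies depends heavily on the unstated threshold. With five independent covariates and 40 per arm, chance alone triggers it in 23% of trials if imbalance means p<0.05 (1 − 0.95⁵ = 0.226). It does so in 78% if imbalance means a standardised difference above 0.25 (each covariate 26.4%; 1 − 0.736⁵ = 0.78).

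At stake are a modest amount of power and the reproducibility of the primary result.

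**Working it through.** The plan states no figure that could be reproduced: 80 participants are given without alpha, power, effect or SD.

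**Inputs.** From the documents: 80 participants, 1:1 allocation, hence 40 per arm if all 80 are enrolled and followed. Assumed: two-sided alpha 0.05; individual randomisation; baseline/follow-up correlation ρ = 0.7, 0.8, 0.9; ratio of follow-up SD to baseline SD λ = 0.9, 1.0, 1.1.

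**Step 1: variance.** With baseline SD σ, the change score has variance σ²(1 + λ² − 2ρλ). Follow-up given baseline has residual variance σ²λ²(1 − ρ²). The ratio, ANCOVA to change score, is

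R = λ²(1 − ρ²) / (1 + λ² − 2ρλ), which equals (1 + ρ)/2 when λ = 1.

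Examples: λ = 1, ρ = 0.8 gives 0.36/0.40 = 0.90; λ = 1.1, ρ = 0.9 gives 0.2299/0.23 = 1.00.

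**Step 2: power.** The t-test (df 78) has 80% power at a difference of d = 0.634 SD of change, with noncentrality 0.634 × √(40/2) = 2.84. For ANCOVA with k covariates, divide the noncentrality by √(R × [1 + k/(80 − k − 3)]), where the bracket allows for chance imbalance, and use df 78 − k. For λ = 1, ρ = 0.8, k = 1: 2.84/√(0.90 × 1.0132) = 2.97 on 77 df, or 83.5%.

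| λ | ρ | R | Power, baseline waist only | Power, plus two uninformative covariates |
|---|---|---|---|---|
| 0.9 | 0.7 / 0.8 / 0.9 | 0.751 / 0.788 / 0.810 | 89.5 / 88.0 / 87.1% | 88.6 / 87.1 / 86.2% |
| 1.0 | 0.7 / 0.8 / 0.9 | 0.850 / 0.900 / 0.950 | 85.5 / 83.5 / 81.5% | 84.6 / 82.5 / 80.4% |
| 1.1 | 0.7 / 0.8 / 0.9 | 0.921 / 0.968 / 1.000 | 82.6 / 80.7 / 79.5% | 81.6 / 79.7 / 78.4% |

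**Step 3: smaller samples.** Take the worst cell (λ = 1.1, ρ = 0.9, three covariates) and reset d so that the t-test again has 80% power. Power is then 77.8% at 30 per arm and 76.4% at 20 per arm.

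**Step 4: type I error of the trigger.** This was simulated with N = 80 and 20,000 trials per setting (Monte Carlo SE about 0.15 points at 5%). There were 4 to 6 independent baseline covariates, each with the correlation shown with the outcome.

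| Correlation | Rule applied mechanically: p<0.05 trigger | Mechanically: standardised difference >0.2 | Better of t-test and triggered model: p<0.05 | Better of the two: >0.2 |
|---|---|---|---|---|
| 0.1 | 4.8-4.9% | 4.6-4.8% | 5.1-5.4% | 5.8-6.4% |
| 0.2 | 4.3-4.8% | 3.7-4.1% | 5.1-5.7% | 6.2-6.5% |
| 0.3 | 3.7-4.0% | 2.2-2.9% | 5.2-5.6% | 6.0-6.3% |

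A fixed covariate model held 4.8-5.2% throughout. The mechanical rule is conservative because it removes covariate-driven differences exactly where they are large. It leaves the unadjusted standard error, which still allows for them, where they are small. A second simulation with other settings (six covariates including baseline waist, ρ 0.5-0.9, threshold p<0.05 or 0.25) gave 3.2-4.6% for the mechanical rule and 5.3-6.4% for the better of the two.

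**The case against.** The strongest reply is that this is a pilot with no stated alpha or power, the change-score t-test is valid under individual randomisation, and adjusting for observed imbalance is common practice. The trigger concerns baseline data, not outcomes, and the natural reading is that the adjusted model takes over once imbalance is seen. All of that stands, and it limits the weight of the point. It does not supply the missing threshold, covariates or ranking of results.

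A reader might infer more than the documents support, in three ways.

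- *That the clause inflates type I error.* Followed as written, it does the opposite. Inflation needs an analyst who picks the better p-value, and even then it is at most about 1.5 points. Larger figures require a free search over covariate subsets, whereas 5c confines adjustment to the imbalanced covariates.
- *That baseline adjustment always gains power.* In the least favourable cell it loses a little, and the loss grows in smaller samples. Forty per arm is optimistic: two-thirds of 140 infusion patients is about 93 with qualifying body mass index before exclusions and refusals.
- *That the t-test is shown to be valid, or invalid, for this trial.* Neither is settled. Study Procedures 2a says allocation is "stratified by week of enrollment, to receive electronic adherence support or to the standard of care", while 2c describes clustering by the week of the baseline visit, and the stated aim of avoiding talk between patients infused together fits the second better. If whole weeks share an arm, the plain t-test is too liberal. With an assumed intraclass correlation of 0.05-0.10 and 4-10 patients per week, the design effect 1 + (m − 1)ICC runs from 1.15 to 1.90. The true level of a nominal 5% test is then about 6.8% to 15.5% (1.96/√1.15 = 1.83; 1.96/√1.90 = 1.42). That is a separate and possibly larger issue, and none of the figures in the working would then apply.

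**Conclusion.** The point holds as a cheap improvement, not as a validity flaw. Given individual randomisation, the planned analysis is valid but less efficient than ANCOVA in most plausible settings, and its primary result is not uniquely defined.

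At equal SDs the gain is 1.5 to 5.5 points of power from a base of 80%. Over the whole grid, with baseline waist alone, it ranges from a loss of 0.5 to a gain of 9.5 points. The mechanical trigger costs type I error that could have been used (about 2-5% against 5%); choosing between results gives about 5-6.5%.

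The alpha, correlations, SD ratios, covariate numbers and thresholds are assumptions, since the documents give none. I am confident of the gap in the text, less so of its size, which depends on how the randomisation is carried out.

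**What to change.** Delete the imbalance trigger from 5c and prespecify one primary model for the calorie restriction study: waist circumference at one named visit (month 3 or month 6) regressed on arm and baseline-visit waist, plus at most a short fixed list of pre-randomisation covariates such as age and sex. Analyse weight and body mass index in the same way, each with its own baseline. Percentage adherence has no baseline value, because the application is first installed at the baseline visit. Keep the unadjusted t-tests as sensitivity analyses.

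Before finalising the model, reconcile 2a and 2c on whether week is a stratum or a cluster. If whole weeks share an arm, the primary model must also allow for clustering by week.

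**Cost.** No new data, one to three degrees of freedom and a few sentences of text. In the least favourable case assumed (follow-up SD 1.1 times baseline SD, correlation 0.9), power falls from 80% to 79.5% with baseline waist alone. With two further uninformative covariates it falls to 78.4% at 40 per arm, or to 76.4% at 20 per arm (3.6 points). This argues for keeping the extra covariate list very short or empty if recruitment falls well below 80.
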